## 8.3 Number of Subjects

- If this is a multicenter study, specify the number of subjects to be enrolled in total across all sites. 220.
- Specify the number of subjects to be enrolled at the Tufts site. Subjects who sign an ICF are considered "enrolled". For studies that have a separate screening ICF, this number is the number of subjects who sign a screening ICF. 100
  - Provide the rationale for enrolling this number of subjects at the Tufts site.
     This is approximately 50% of the study recruitment goals of 200. In addition to the already recruited participants in Cleveland and Baton Rouge, the Boston sites anticipate to recruit the remaining subjects to meet the goals.
  - Estimate the number of subjects expected to be enrolled at the Tufts site (i.e. sign the screening or study ICF) as well as the number needed to complete the study at the Tufts site.
     We anticipate recruiting 100 subjects in the Greater Boston area and expect a 40 to 50% dropout for various reasons.
  - If a large number of withdrawals and/or dropouts are expected, explain why.
     It is not unusual for a lifestyle intervention study lasting over a number of years to have a 40% dropout rate. This has been addressed in the statistical analysis.

#### 8.4 Data Management

- Describe the data analysis plan, including descriptions of the data. This is described in the statistical analysis
- *Provide a power analysis.*

This is included in the statistical analysis.

- Describe the steps that will be taken to secure the data (e.g., training, authorization of access, password protection, encryption, physical controls, certificates of confidentiality, and separation of identifiers and data) during storage, use, and transmission.
   All research staff for the LIPP grant has undergone CITI training and have research experience. The PI of the project has 30 years of clinical research training and has not had any research violations of authorization of access, password protection, encryption, physical controls, certificates of confidentiality, and separation of identifiers and data during storage, use, and transmission. We anticipate that the study coordinator of the LIPP grant will have as a minimum a Bachelor's degree and clinical research experience.
- Describe any procedures that will be used for quality control of collected data.

The Study coordinator, the PI and Statistical staff will ensure that the data has been collected and cleaned appropriately. Any data that is judged to be an outlier will be reassessed going back to the original source. In the past we have reanalyzed approximately 10% of data to make sure that results are consistent with first time analyses.

- Describe how data and specimens will be handled study-wide:
  - What information will be included in that data or associated with the specimens. The non-PHI study subject identifier as well as which visit the data was collected will be noted and entered into REDCap.
  - Where and how data or specimens will be stored.
     Data will be stored on REDCap. Hard copies will be maintained in a locked cabinet in a locked office of the study coordinator.
  - How long the data or specimens will be stored.
     Until the study is completed. Hard copies will be kept as long as the data are being analyzed.
     Non-PHI data will be stored on an encrypted hard drive.
  - Specify who will have access to the data or specimens.
     The PI, study coordinator and staff in the HNRCA and BWH Research Facility will have access to the data. The statistical staff and REDCap team will have access to the non-PHI data.
  - Specify who is responsible for receipt or transmission of the data or specimens. The study coordinator and PI.
  - Specify how data and specimens will be transported. By research staff from the LIPP, BWH Research Facility, MIRI and HNRCA.
  - Specify the plan for study data retention and storage (accounting for research team turnover). The PI will maintain the data along with [name] the MPI at the Pennington.

# 8.5 Randomization

Will subjects be randomized?

# 🗹 Yes 🛛 No

If **Yes**, describe the following:

- *The randomization procedures, including the ratio of subjects randomized to each study arm.* Yes through a computer generated randomization stratified for overweight vs. obese and breastfeeding status.
- *The blinding procedures if the study will be blinded.* N/A, only the statistician analyzing data will be blinded.

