# 5 Study Design

# 5.1 Study Timelines

- Describe the duration of an individual subject's participation in the study.
  - The time that the subject will be in the study is variable. The minimum time is 13 months (4 months in study and 9 months of pregnancy). The maximum time is 28+ months. The pre-pregnancy component of the study is variable. We list 18 months in study/21 months post-partum but if the subject becomes pregnant after 21 months post-partum, she will be followed in the pregnancy component. Hence, we list 28+ months.
- Describe the duration anticipated to enroll all study subjects at the Tufts study site. Subjects will have their initial testing and randomization 3 calendar months (+/- 3 full weeks) after their delivery. Enrollment begins when the Informed Consent is signed.
- Describe the estimated date for investigators to complete this study (complete primary analyses). The initial grant ended on 11/30/2022 and we are on an approved no-cost extension until 11/30/2023.
- Describe the study procedures that will be accomplished at each study visit. At the HNRCA, CTRC or BWH Research Facility, the following metabolic testing/procedures will be performed:

Metabolic evaluations will be performed at baseline (3 months  $\pm$  3 full weeks postpartum). Follow-up evaluations will be performed after 6 ( $\pm$  3 full weeks) and 9 months ( $\pm$  3 full weeks), 15 ( $\pm$  3 full weeks) and 21 months ( $\pm$  3 full weeks) prior to pregnancy (Figure at the top of the protocol form) up to a maximum of 18 months. Once a subject becomes pregnant and has dating and viability confirmed by ultrasound, metabolic evaluations will continue at 12-16 and 32-36 weeks of gestation. However, if an individual participant has scheduling issues or there are extenuating circumstances with scheduling visits, we may schedule outside of the above windows.

Maternal Body Composition: Anthropometry measurements will include height, weight, and hip and waist circumferences. Total body fat will be measured by whole body plethysmography (Bod Pod; Cosmed, Rome, Italy), (70). We will use a hydration constant of 76% for fat free mass during late pregnancy (71). If a BodPod is not available we will use skin calipers to take skinfold measurements of the triceps and mid-axillary skinfold to estimate body fat.

Resting Energy Expenditure: Resting Metabolic Rate (RMR) will be determined after an overnight fast using the Cosmed OMNIA metabolic cart (Cosmed, Rome Italy) with a

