#### 8.2 Statistical Analysis

• Describe the statistical analyses that will be performed for this study **Statistical Analysis** 

The primary analyses of Specific Aim 1a will be intent-to-treat comparisons of the LIPP and Control groups in regard to changes in maternal insulin sensitivity, BMI, and fat mass. The comparisons will be performed first with two-sample t-tests at  $\alpha$ =0.05. Should any imbalance of confounding factors in the groups be recognized, linear regression models that include significant differences (e.g. GDM) would be used to perform covariate adjustments. Based on our 1-year postpartum follow-up studies (62,63), we will have 90% power to detect an absolute or covariate-adjusted improvement in insulin sensitivity of 30% and an 80% power to detect an improvement as small as 25% in the LIPP vs. Control group. Corresponding 95% confidence intervals (95% CI) for the absolute or covariate-adjusted differences or percent improvements in insulin sensitivity between groups will be reported. We estimate the standard deviation (SD) of change in BMI from randomization until subsequent pregnancy to be 5.1 kg/m2. We will have 90% power to detect an absolute or covariate-adjusted difference in BMI of 2.6 kg/m2 and 80% power to detect a difference of 2.26 kg/m2 and 90% power to detect an absolute or covariate-adjusted difference in fat mass of 5.9 kg and 80% power to detect a difference of 5.1 kg between groups prior to the second pregnancy. The primary analysis for Specific Aim 1b is an intent-to-treat comparison of LIPP versus Control neonates with respect to fat mass at birth. The comparison will be performed using a two-sample t-test at  $\alpha$ =0.05. Linear regression will be performed, which will include weight (body composition measures) of the subject's index child as a covariate. Should any imbalance of confounding factors (for example gestational age) in the groups be recognized, linear regression models will be used to perform a covariate adjustment. Based on our preliminary data, we estimate the SD of neonatal fat mass between the LIPP and Control groups to be no more than 225 g. With at least 50 women in each group, (assuming a 50%) dropout), the t-test or linear regression will have 90% power to detect an absolute or

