## Section 5.1 Study Design

- *Resting Energy Expenditure* 
  - Resting Metabolic Rate (RMR) will be determined after an overnight fast using a Deltatrac II indirect calorimeter (Datex-Ohmeda, General Electrics, Finland) with a canopy system.
- Neonatal Measures
  - A PEAPOD is housed at Pennington Biomedical Research Center.
  - Pennington Biomedical staff will perform requisite tissue collection at local Baton Rouge hospitals dependent on where the participant delivers (Legal agreements are provided for Baton Rouge General and Women's Hospital, while the Ochsner legal agreement is pending). After hospital discharge, participants will travel to Pennington Biomedical where a PEAPOD measure and neonatal anthropometrics will be performed. If travel is difficult, neonatal anthropometrics may be obtained at respective hospitals.

- Additionally, a medical release form will be obtained from the participant for the purpose of obtaining the antenatal chart.
- Finally, neonatal anthropometrics, caliper measurements and circumference measures may be conducted at the houses of PBRC-enrolled study participants if they are unable to travel to the PBRC site after delivery.
- Lifestyle Intervention Group
  - Supervised Exercise Intervention
    - Exercise sessions will be conducted at Pennington Biomedical Fitness Center by the Intervention Resources Department at Pennington Biomedical. (See additional descriptions below.)

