#### Section 5.3 Evaluations

- All laboratory tests will be performed by the Pennington Biomedical Clinic, [name] Lab Team and/or analyzed by the Clinical Chemistry Core at Pennington Biomedical. (See additional descriptions below.)
- Sample Handling & Storage
  - Sample processing and storage will occur locally at PBRC, following the description in the parent protocol.
- Cord blood collection and placenta collection at delivery
  - This process is described in detail in our Standard Operating Procedures (SOP 2304 Placenta Collection and Processing). In brief, LIPP research staff ([name]) will collect tissue specimens from the research participant's delivering hospital. Samples will be collected according to protocol and placed on ice or liquid nitrogen. The samples will then be immediately transported by [name] to PBRC for further processing and storage by LIPP staff ([name] Lab personnel) until analysis. The clinical chemistry core will perform glucose and lipid profiles on cord blood samples. When the research participant is admitted to their delivering hospital's delivery unit, they will hand the PBRC Placental Biospecimens Delivery Unit Information sheet to the attending physician.

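### Site is neither a named randomisation stratum nor a term in any planned model; adding it in advance would be a cheap, modest gain, mainly for neonatal fat mass

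*Combined protocol and SAP*

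**What the plan says.** Section 8.5 gives the allocation method: "Yes through a computer generated randomization stratified for overweight vs. obese and breastfeeding status". It does not say whether lists were central or held by site.

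For the primary outcome, neonatal fat mass (Aim 1b), section 8.2 states: "The comparison will be performed using a two-sample t-test at" the 0.05 level. It continues: "Linear regression will be performed, which will include weight (body composition measures) of the subject's index child as a covariate". Other covariates are conditional: "Should any imbalance of confounding factors (for example gestational age) in the groups be recognized", regression would be used to adjust. Aim 1a has a parallel clause with gestational diabetes as its example, and the Aim 2 regression names gestational age and gender. Site appears in none of these.

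Three areas contribute women. Section 8.3 refers to participants already recruited in Cleveland and Baton Rouge, with Boston supplying the remainder. The documents record these differences between them:

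- **Newborn measurement.** In Baton Rouge, mothers travel to Pennington after hospital discharge for the PEAPOD, with hospital or home anthropometrics if travel is difficult (addendum 11.1). In Boston, the Pea Pod is at Tufts (section 5.1) and anthropometrics stand in where no device is available (section 10.3).
- **Recruitment.** Tufts approaches women on the postpartum unit (section 4.4.1). Baton Rouge also used web advertising, flyers and community events (addendum 11.1).
- **Calendar period.** Baton Rouge has closed to recruitment while Brigham and Women's continues (section 4.4.2).

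**The concern.** When outcome means differ between sites and the analysis ignores site, the between-site variation stays in the error term. Any chance difference in site mix between arms then shifts the estimated effect. With about 50 newborns per arm, such differences in mix are not rare.

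Neonatal fat mass is the exposed outcome. It is measured once and has no baseline of its own, so a constant offset between sites does not cancel as it largely would in the Aim 1a change comparisons.

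The conditional clause in section 8.2 does not settle the matter. It could admit site, but only after someone has inspected the arms and judged an imbalance worth acting on, so the final model would depend on what was seen.

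**Working it through.** **Inputs from section 8.2.** The SD: "we estimate the SD of neonatal fat mass between the LIPP and Control groups to be no more than 225 g". There are 50 women per arm after 50% dropout. The stated detectable differences are 146 g (90% power) and 126 g (80% power). A two-sided 0.05 test and equal allocation are assumed, because neither is stated.

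**Reproducing the plan's figures.** Detectable difference = (z for alpha + z for power) × SD × √(2/n).

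- 90% power: 3.2415 × 225 × √(2/50) = 145.9 g
- 80% power: 2.8016 × 225 × 0.2 = 126.1 g

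Both match. In the other direction, 146 g gives 90.1% power and 126 g gives 80.0% (noncentral t: 89.5% and 79.2%). The calculation contains no site component.

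**Assumptions the documents cannot supply.** Take two sites with mean difference D and smaller-site share q. Section 4.1 planned 100 women each for Boston and Baton Rouge. However, section 4.4.1 mentions 20 recruited in Cleveland and addendum 11.1 mentions 12 enrolled at Pennington to date, and either count may be out of date. A range of q from 10% to 50% is therefore shown. No between-site difference is reported, so D runs from 50 to 200 g.

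**Effect on power.** The meaning of 225 g decides the direction.

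- *225 g is the within-site SD.* Ignoring site raises the SD to √(225² + q(1−q)D²). For q = 50% and D = 100 g this is √(50,625 + 2,500) = 230.5 g. Then 146/(230.5 × 0.2) − 1.96 = 1.21, which gives 88.6% power.
- *225 g is the total SD.* The unadjusted power is as stated. Adjusting lowers the SD to √(225² − q(1−q)D²), for the same case √(50,625 − 2,500) = 219.4 g, which gives 91.4% power.

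| q | D (g) | 225 within site, site ignored: power at 146 / 126 g | 225 total, site adjusted: power at 146 / 126 g | SD of chance shift (g) |
|---|---|---|---|---|
| 10% | 50 | 89.9 / 79.8% | 90.2 / 80.1% | 3.0 |
| 10% | 100 | 89.5 / 79.3% | 90.6 / 80.7% | 6.0 |
| 10% | 200 | 88.0 / 77.2% | 92.0 / 82.8% | 12.1 |
| 50% | 50 | 89.7 / 79.5% | 90.4 / 80.4% | 5.0 |
| 50% | 100 | 88.6 / 78.0% | 91.4 / 81.9% | 10.1 |
| 50% | 200 | 84.3 / 72.5% | 95.2 / 87.8% | 20.1 |

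The reference is 90.1 / 80.0%. In the within-site case the loss is therefore 0.2 to 5.8 points at 146 g and 0.2 to 7.5 points at 126 g.

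**Chance imbalance.** Drawing 50 per arm at random from 100 newborns, the difference in site share between arms has SD 2√(q(1−q)/99). That is 0.10 at q = 50% and 0.06 at q = 10%. Multiplying by D gives the last column. A difference of 20 points or more has about a 7% chance at q = 50% and about 0.1% at q = 10%. The chance shift averages zero. It and the loss of power are two views of the same variance, so they should not be added together.

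**The case against.** The strongest reply is that the primary inference is not in error. Under randomisation a site imbalance has expectation zero and the t-test holds its level on average. Section 8.2 already plans one regression covariate, and its imbalance clause is open-ended enough to admit site. All of this stands. It limits the point to precision and pre-specification, but it does not make the conditional clause a plan for site.

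A reader might infer that site differences contaminate every arm comparison. The documents do not support that:

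- **Laboratories.** Addendum 11.1 says of Baton Rouge: "All laboratory tests will be performed by the Pennington Biomedical Clinic". Section 5.3, however, sends insulin, C-peptide and incretin samples to Pennington, and inflammatory markers and placental samples to Tufts or Brigham and Women's. Most metabolic and placental assays are thus centralised or shared.
- **Calorimeters.** Boston measures resting metabolic rate "using the Cosmed OMNIA metabolic cart (Cosmed, Rome Italy) with a" canopy, and Baton Rouge does so "using a Deltatrac II indirect calorimeter (Datex-Ohmeda, General Electrics, Finland) with a canopy system". Resting metabolic rate is not among the section 8.1 endpoints; energy expenditure appears only in the Sub-Aim 1a hypothesis. Its use in setting calorie needs concerns delivery in one arm, which a site main effect would not correct.

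Two further limits stand. Newborn measurement also varies within Boston, so a site term captures only part of that variation. And if randomisation lists were site-specific, site was balanced at allocation. Addendum 11.1 lists randomisation assignment among local staff duties, which does not settle the question. Even then site belongs in the model, because otherwise the error term keeps variation that the design removed from the comparison.

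**Conclusion.** The omission is clear from sections 8.5 and 8.2, and a pre-specified site term is better than the stated approach. The gain is modest. Over the assumed ranges (D 50–200 g, q 10–50%), ignoring site costs about 0.2 to 6 points of power at 146 g if 225 g is the within-site SD. If 225 g is the total SD, nothing is lost against the stated power, and adjustment would raise it to between 90.2% and 95.2%. The top of the range is demanding: a site difference of 200 g exceeds the 146 g treatment effect sought.

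It would be too strong to conclude that the primary comparison is systematically biased by site. That would require, for example, retention that differs by arm and site together, and the documents give no data on this. The point applies mainly to neonatal fat mass, and less to centrally assayed outcomes and the Aim 1a change scores. It is a cheap improvement.

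**What to change.** Before any arm data are compared, amend section 8.2 so that:

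1. The primary model for neonatal fat mass is a linear regression on arm with site (Cleveland, Baton Rouge, Boston) as a fixed effect, the two stratification factors (overweight/obese and breastfeeding status) and the index-child covariate already planned. This applies whether or not any imbalance is seen.
2. The other between-arm models in section 8.2 carry site and the two stratification factors in the same way.
3. Neonatal fat mass is reported by site descriptively.

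In section 8.5, state whether the randomisation lists were site-specific.

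The cost is wording plus four degrees of freedom beyond the planned covariate (two for three sites and one for each binary factor), out of 98 for a t-test on 100 newborns. No new data are needed.

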# PROTOCOL TITLE: Lifestyle Intervention in Preparation for Pregnancy (LIPP) VERSION DATE: March 31st, 2023

• Describe the steps that will be taken to make the subjects feel at ease with the research situation in terms of the questions being asked and the procedures being performed. "At ease" does not refer to physical discomfort, but the sense of intrusiveness a subject may or may not experience in response to questions, examinations, and procedures.

The consent form will describe the study procedures in detail. The study protocol will be explained to the subjects as well. At the time of the visit, the LIPP study staff (PI when available and study coordinator) in addition to the CTRC, HNRCA or BWH Research Facility staff will be present to answer any ongoing questions. For those subjects randomized to the intervention group, HNRCA or BWH Research Facility staff will be present during the visit as well as the training sessions. Hence, there will be continuity of staff with all subjects in the LIPP study.

• Under what circumstances will the research team access sources of information about the subjects. The only time the LIPP research team will access sources of information about potential subjects is when the postpartum delivery records are screened for subject eligibility and the outcome pregnancy and delivery.

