#### Event Relatedness

Related: The incident, experience, or outcome is more likely than not caused by study procedures.

- A reasonable time course would be within the 1-4 hours the subject is receiving oral glucose tolerance testing.
- Symptoms abate once the study product is discontinued and patient has received a snack or drink. Symptoms are not explained by other factors such as concomitant medications or current illness

*Possibly Related:* There is reasonable possibility that the incident, experience or outcome may have been caused by study procedures.

• A reasonable time course would be within 24-48 hours the subject either fasting for the study or receiving the oral glucose tolerance testing.

or

• Symptoms may be explained by other factors such as concomitant medications or current illness

Adverse Event	
VO 2 max	Falling off treadmill
VO 2 max	Exhaustion
VO 2 max	Feeling like heart is pounding very fast very hard

VO 2 max	Dizziness
VO 2 max	Heart rhythm abnormalities
VO 2 max	Chest pain
VO 2 max	When the mask is on the face, this might feel uncomfortable
Structured exercise	Feeling like heart is pounding very fast or very hard
Structured exercise	Dizziness
Structured exercise	Heart rhythm abnormalities
Structured exercise	Chest pain
Laboratory studies	Bruising at IV site
OGTT	Nausea from glucose load
OGTT	Bruising from IV site
Resting Metabolic	
Rate	Claustrophobia
Bod Pod	Claustrophobia
Neonatal	
Anthropometrics	Bruising from skinfold calipers
Maternal	
anthropometrics	Bruising from skinfold calipers

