## **10.3** Resources Available

• Specify the role and tasks delegated to each research team member.

Pennington Biomedical Research Center – Research team members will perform analysis of data, and interactions with participants during recruitment, evaluation in the clinical research unit, for nutrition, and for lifestyle changes. Please see addendum for site specific procedures.

Massachusetts General Hospital & Brigham and Women's Hospital-- Potential participants will be recruited from eligible women who have delivered infants at MGH and BWH. TMC study staff will reach out by email, phone, or mail to women who agree to be contacted at a later date and will offer study participation. Consent and all subsequent study procedures will be conducted at Tufts Medical Center or

Brigham & Women's Hospital for those women who elect to participate. Cord blood and placental collection will be done according to standard of care at the respective hospitals. BWH or MGH LIPP research staff will collect designated tissue specimens from the research participant's hospital. Samples will be collected according to protocol, aliquoted and processed as needed and placed on ice or liquid nitrogen. The designated samples will either be transported to TMC/MIRI for further processing and storage by LIPP staff until analysis or processed and stored at BWH until analysis. Neonatal anthropometrics will be performed at the institution by LIPP staff and be used as an alternative measure for body fat if a PeaPod is not available. Neonatal anthropometrics may be conducted at the houses of LIPP participants with their consent if a participant delivers at a facility other than an approved LIPP study site and are unable to travel to BWH, MGH or TMC after delivery. Both anthropometrics and PeaPod will be performed otherwise. Additionally, for those participants who deliver at BWH or MGH, LIPP research staff will conduct study sample collection according to the site protocol. In addition to infant measures and study sample collection, LIPP study staff will conduct maternal questionnaires prior to delivery and post-delivery. Before delivery, the Infant Feeding Intention Scale will be conducted; after delivery, questionnaires will include the Breast-Feeding Self-efficacy after Delivery, Infant Feeding Practices Scale and the Holmes-Rahe Life Stress Inventory.

• At Tufts Medical Center;

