#### Interventional Resources Expertise including Facilities, Equipment, & Resource Descriptions

#### **Fitness Center**

Pennington Biomedical includes a 2300-square-foot Exercise Training Facility. The facility offers state-of the-art equipment, professional intervention technicians, and optimal training data-capturing capabilities. Staff have the ability to collect and enter data in real-time via a standing desk with dual monitors to operate the heart rate software, databases, and drive files as needed. The cardiovascular fitness training room contains 12 treadmills, 6 stationary bikes, and 2 elliptical while the strength training room has an extensive set of machines and free weights. There are 3 private rooms for intervention related counseling in a one-on-one or small group setting. For measurements, there's a private exam room complete with scale, stadiometer, and computer. In addition, there's a meeting room space capable of outfitting group exercise classes, group presentations, study orientations or introductory sessions, or childcare facility for study participants. The Fitness Center is supported by a trained staff composed of full-time exercise interventionists and students working on exercise-related degrees.

The facility is participant friendly and includes televisions, reading materials and enthusiastic staff who are well trained in customer service. Further, there are locker rooms equipped with lockers and showers available exclusively

for the use of study participants. The facility has a defibrillator, electronic scales, and multiple heart rate monitors systems (Polar and Zephr Bioharness). There is an outdoor walking track as well. The scenic walking track is 12 feet wide, paved, lighted and well-maintained. While the track is over half a mile in length there are 3 intermediate circle turn-outs that can be used to create shorter walking courses. All exercise intervention areas at Pennington are located in buildings far from the clinical assessment area with virtually no opportunity for assessment staff to accidentally observe exercising participants.

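### Section 8.5 masks only the statistician, so no masking is planned for the staff who measure the newborn, and the primary outcome is most exposed where skinfolds replace the Pea Pod

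*Combined protocol and SAP*

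**What the plan says.** Section 8.5 answers the blinding question with "N/A, only the statistician analyzing data will be blinded". No other section of the protocol provides for a masked assessor.

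Section 8.1 states the primary outcome in one direction, as lower adiposity at birth in the LIPP arm. Section 8.2 analyses it as fat mass at birth, with a two-sample t-test at the 0.05 level.

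On who measures, section 10.3 says "Neonatal anthropometrics will be performed at the institution by LIPP staff", and that these measures will "be used as an alternative measure for body fat if a PeaPod is not available". The same section allows them at the participant's home after delivery elsewhere if she cannot travel, and says that otherwise both anthropometrics and Pea Pod are done. The Pennington addendum (section 11.1, neonatal measures) also allows anthropometrics in the delivery hospital or at home when travel is difficult. The adverse event table in section 7.1 confirms that calipers are used on newborns: under neonatal anthropometrics it lists "Bruising from skinfold calipers".

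**The concern.** A skinfold reading depends on where the caliper is placed and how it is read. An assessor who knows the arm and expects leaner LIPP babies can shift the derived fat mass towards the hypothesis without meaning to. Such an error differs by arm, so a larger sample does not average it out. Masking the statistician does not help, because the error is in the data before analysis starts.

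Study staff have several ways to learn the arm. Under section 4.3, the monthly calls to women not yet pregnant at 21 months include a weight-goal reminder for the intervention arm only. Under section 4.4.3, the payment schedules differ by arm, and the gift card given once the baby has been measured is listed only for the LIPP arm.

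At stake is the credibility of the main comparison in a trial where neither participants nor intervention staff can be masked. The newborn measurement is the step at which masking is most feasible.

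**Working it through.** **Inputs, all from section 8.2:** SD of neonatal fat mass at most 225 g; at least 50 per arm after an assumed 50% dropout; alpha 0.05. Sidedness is not stated; two-sided is assumed, and it reproduces the plan's figures.

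**Plan's own figures.**
- Standard error of the arm difference: 225 × √(2/50) = 45 g.
- Detectable difference at 90% power: (1.960 + 1.282) × 45 = 145.9 g (stated: 146 g).
- Detectable difference at 80% power: (1.960 + 0.842) × 45 = 126.1 g (stated: 126 g).

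The power statement is sound and is not the issue.

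**Effect of a spurious shift.** Let d be the net shift in the arm difference, averaged over all infants, with no true effect. The two-sided rejection rate is 1 − Φ(1.96 − d/45) + Φ(−1.96 − d/45). The documents give no value for d, so the range is assumed.

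| Assumed net shift d | d/45 | Two-sided error | Error in the hypothesised direction (nominal 2.5%) |
|---|---|---|---|
| 10 g | 0.222 | 5.6% | 4.1% |
| 20 g | 0.444 | 7.3% | 6.5% |
| 40 g | 0.889 | 14.4% | 14.2% |

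**What a net shift requires.** If the bias arises only in infants with skinfolds alone, and they are a fraction f of all infants, then d = f × (bias in those infants). The documents do not give f. Two assumed values:
- f = 25%: a 10 g net shift needs 10/0.25 = 40 g in those infants; a 40 g net shift needs 40/0.25 = 160 g, more than the 146 g difference the trial is powered to detect.
- f = 50%: the same net shifts need 20 g and 80 g.

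The 40 g row is therefore close to a worst case unless skinfolds supply the outcome for a large share of infants.

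**The case against.** The strongest reply is that skinfolds are only the fallback. Section 10.3 has both measures taken when a Pea Pod is available, and the Pea Pod is probably less dependent on the operator. This stands and limits the size of the problem. It does not remove it: the share with skinfolds only is unknown, and section 8.2 does not say which measure is analysed when both exist. Pea Pods are located only at Tufts Medical Center (section 5.1) and Pennington (section 11.1). None is described at Brigham and Women's, where recruitment continues (section 4.4.2), though the documents do not say there is none.

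It is also fair to say that an absence of planned masking does not prove that every measurer knows the arm. The point is that nothing in the plan prevents it.

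Three stronger readings are tempting, and the documents do not support them:
- A reader might infer that the Boston staff who run training also measure the newborns. Section 6.5 says "HNRCA or BWH Research Facility staff will be present during the visit as well as the training sessions" and adds "Hence, there will be continuity of staff with all subjects in the LIPP study". That text concerns putting women at ease at study visits. Section 10.3 speaks only of LIPP staff at the delivery hospital, and nowhere are the two groups identified as the same people.
- A reader might infer that Pennington masks its assessors and Boston has given this up. The Pennington facility text does claim "virtually no opportunity for assessment staff to accidentally observe exercising participants", but it describes building layout, not newborn measurement in hospitals or homes. The resource descriptions that follow give the same Pennington staff both assessment data collection and delivery of the interventions.
- A reader might extend the point to the treadmill tests. The protocol says nothing about staff encouragement in them, and exercise capacity is not among the section 8.1 endpoints.

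**Conclusion.** The point holds in a limited form. Section 8.5 restricts masking to the statistician, no section masks the newborn assessor, and a caliper-based measure can supply the primary outcome. This is an avoidable source of bias, not a fatal flaw.

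Its size cannot be established from the documents. The error rates of 5.6% to 14.4% illustrate what assumed net shifts of 10 to 40 g would do at a standard error of 45 g; they are not estimates of the trial's actual error. They rest on 50 analysed infants per arm and an SD of 225 g. The plan gives that SD as an upper limit, and a smaller SD would make the same shift matter more. The lower end of the range is the more plausible if most infants have a usable Pea Pod value that is the one analysed.

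**What to change.** For remaining births, change section 8.5 to say that the statistician is masked and that neonatal Pea Pod and anthropometric measurements are made, wherever existing rosters allow, by existing study staff who have not coached or trained that woman and are not told her arm. In support:
- Ask mothers not to disclose their group until the measurements are recorded.
- Keep the arm off the neonatal data forms.
- If only an unmasked person is available, measure anyway, so that no infant is lost.
- Record for every infant the masking status and the method (Pea Pod or skinfold).
- Add to section 8.2 a sensitivity analysis restricted to Pea Pod or masked measurements, and report the method by arm. This subset is smaller and not randomly chosen, so it should support the full intent-to-treat comparison, not replace it.

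Sample size, visits and procedures do not change, and no extra assessor is required. The cost is less scheduling flexibility around unplanned deliveries. Staff rosters are not in the documents, so how often a masked person will be free at each site is unknown, which is why the unmasked fallback is needed. Newborns already measured cannot be masked in retrospect. For them, only the restriction to Pea Pod values can help, provided the method was recorded.
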